**AE Stop Date:**

Ongoing events will have the AE Stop Date set to one of the following values:

- Date of Death, if the patient died and a date of death exists.
- Maximum of (Patient Withdraw date, AE Onset Date, AE Collection Date) if the patient withdrew from the study and a date of withdraw exists.
- Maximum of (AE Onset Date, Subject Summary Collection Date, AE Collection Date) if the Disposition CRF page for the long-term follow-up phase exists but a date of completion/discontinuation does not exist.
- Maximum of (Last Treatment Date, AE Onset Date) if no Disposition CRF page for the long-term follow-up phase exists.

Imputation will only occur if event is unique for the patient, or it is the last of a series of similar events; otherwise the Stop Date will not be imputed. Adverse Events are deemed similar if they have the same verbatim term.

Resolved events will have the AE Stop Date set to the maximum of the AE collection date and the AE Onset date.

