### **8.1.4. Time Period for Collecting AE/SAE Information**

The time period for actively eliciting and collecting AEs and SAEs (“active collection period”) for each subject begins from the time the subject provides informed consent, which is obtained before the subject’s participation in the study (ie, before undergoing any study-related procedure and/or receiving investigational product), through and including a minimum of 28 calendar days after the last administration of the investigational product.

For subjects who are screen failures, the active collection period ends when screen failure status is determined.

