## 5.3. Methods to Manage Missing Data

Unless otherwise specified, all data will be evaluated as observed, and no imputation method for missing values will be used.

Any imputations will occur at the analysis dataset level. Additionally, in all patient data listings imputed values will be presented and flagged as imputed.

Missing statistics, eg, when they cannot be calculated, should be presented as 'ND' for not done, 'NR' for not reached or 'NA' for not applicable. For example, if N=1, the measure of variability cannot be computed and should be presented as 'ND' or 'NA'.

CDISC Safety Rulebook will be followed when handling the missing/partial dates, treatment emergent AE algorithm, missing AE grades, etc.

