### 6.6.1.3. Adverse Events of Special Interest

These analyses will be performed for treatment emergent AEs of special interest as specified in 3.5.1.

- **Time to AE Onset** (in days) is defined as the time from the date of the first dose to the onset date of the AE, regardless of grade. If a patient has multiple episodes of an AE, the date of the first occurrence is used. Time to AE onset (in days) will be calculated as (AE start date – first dose date +1). Time to onset is calculated for the subgroup of patients who had the specific AE.
- **Time to Grade 3 or 4 AE Onset** (in days) is defined similarly as time to AE onset for Grade 3 or 4 AEs.
- **Duration of AE** (in days) is defined as the cumulative duration across episodes of the AE, regardless of grade, where duration for each episode is the time from the AE start date to the AE end date. For one episode, duration (in days) = AE end date – AE start date + 1. If a patient has multiple episodes of an AE, cumulative duration across all episodes will be used adjusting for any overlap. If a patient has an AE that was ongoing at the time of analysis, the time is censored at the last available on treatment visit date. Duration is calculated for the subgroup of patients who had the specified AE.

Descriptive statistics will be presented for time to AE onset (days), time to Grade 3 or 4 AE onset, and duration of AEs for the subgroup of patients with the AE.

Person-year exposure analyses may also be considered in case of relevant difference in treatment duration between treatment arms.

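### SAP 5.3.1 and SAP 6.6.1.3 give conflicting end dates for adverse events recorded as ongoing, and the 5.3.1 date depends on whether the patient died, withdrew or is still in follow-up

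*SAP*

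**What the plan says.** SAP 5.3.1, under the heading AE Stop Date, assigns a stop date to events recorded as ongoing. The date depends on the patient's status:

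- Died: "Date of Death, if the patient died and a date of death exists".
- Withdrew: "Maximum of (Patient Withdraw date, AE Onset Date, AE Collection Date) if the patient withdrew from the study and a date of withdraw exists".
- Long-term follow-up disposition page present but undated: "Maximum of (AE Onset Date, Subject Summary Collection Date, AE Collection Date) if the Disposition CRF page for the long-term follow-up phase exists".
- No such page: "Maximum of (Last Treatment Date, AE Onset Date) if no Disposition CRF page for the long-term follow-up phase exists".

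No branch clearly covers a living patient whose disposition page carries a date. The rule has one limit: "Imputation will only occur if event is unique for the patient, or it is the last of a series of similar events". SAP 5.3 adds: "Any imputations will occur at the analysis dataset level".

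SAP 6.6.1.3 defines the duration of an AE of special interest as end date minus start date plus 1, accumulated over episodes, with descriptive statistics by arm. For an event still ongoing when the analysis is done, it says "the time is censored at the last available on treatment visit date". That rule makes no distinction by vital status.

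On collection, Protocol 8.1.4 has AEs actively collected "through and including a minimum of 28 calendar days after the last administration of the investigational product". Protocol 8.1 extends follow-up until drug-related toxicities have resolved, if that is later. Survival follow-up runs for up to 5 years (Protocol 6.4).

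**The concern.** Two sections of the SAP set an end date for the same kind of record, and they set different ones. Under 5.3.1 two patients with identical AE records can receive different stop dates only because one has died. Because imputed dates sit in the analysis dataset, an event in a patient who died may already carry the death date as its end date when 6.6.1.3 is programmed. It may then no longer be treated as ongoing. The literal wording of 6.6.1.3 points the same way, since a patient who has died has no event still ongoing at the analysis.

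At stake is the by-arm summary of how long AEs of special interest last. If the death date is used, that summary mixes AE duration with survival time, in a trial whose primary endpoint is survival. Two programmers working correctly from this SAP could report different durations for the same event.

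**Working it through.** **How often the death branch could apply.** Planned deaths at the final analysis are 267/400 = 66.8% (intensive) and 220/320 = 68.8% (non-intensive), from SAP 5.1.1.

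To split these by arm, use the SAP's design inputs: exponential survival, a 10-month ramp (taken as linear) to 18 patients per month, and trial durations T of 58 and 37 months. With hazard ln 2/median, the share dead is the average over entry times t of 1 − exp(−hazard × (T − t)).

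- Intensive, medians 21 and 31.5 months: 0.744 control, 0.599 glasdegib. Deaths: 200 × 0.744 + 200 × 0.599 ≈ 269, against 267 planned.
- Non-intensive, medians 10.4 and 16.2 months: 0.775 control, 0.622 glasdegib. Deaths: 160 × 0.775 + 160 × 0.622 ≈ 223, against 220 planned.

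The plan's event counts are reproduced to within 3 or so deaths. Under the design assumptions the death branch is open to about 74% against 60% of intensive patients and 77% against 62% of non-intensive patients (control against glasdegib). These are shares of all patients. The share with an ongoing AE of special interest is not given.

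**What each rule does to one record.** The documents state no AE duration, so there is no figure to reproduce. Assumed days: onset 60, last on-treatment visit 113, last dose 120. The gap from last dose to death is not in the documents and is varied from 14 to 365 days.

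- 6.6.1.3 rule, any patient: 113 − 60 + 1 = 54 days.
- 5.3.1, survivor with no long-term follow-up disposition page: max(120, 60) − 60 + 1 = 61 days.
- Minimum 28-day collection window: 148 − 60 + 1 = 89 days.
- 5.3.1, patient who died: (120 + gap) − 60 + 1 days, as below.

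| Gap from last dose to death (days) | Duration under 5.3.1 (days) | Relative to the 28-day window (days) |
|---|---|---|
| 14 | 75 | −14 |
| 28 | 89 | 0 |
| 60 | 121 | +32 |
| 90 | 151 | +62 |
| 180 | 241 | +152 |
| 365 | 426 | +337 |

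Death within 28 days of last dose produces no excess over the window. The excess passes a month only when death comes about 60 days or more after last dose. At the far end of the range, the same record is 426 days under one rule and 54 under the other.

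**The case against.** The strongest reply is that 6.6.1.3 is the specific rule for the only visible duration analysis, and a specific rule normally overrides a general convention. Read that way, a patient who died and a survivor with the same record get the same duration. If an imputed stop date always closed an event, the censoring sentence in 6.6.1.3 would have almost nothing left to act on, because 5.3.1 imputes dates for survivors too. SAP 5.3 also has imputed values flagged in listings, so an originally ongoing event stays identifiable. This is a reasonable reading and may be what the authors intend, but the SAP does not state it. The 6.6.1.3 wording does not literally reach a patient who has died.

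A second reply is that 28 days is only a minimum. Drug-related toxicities are followed until they resolve, so time up to death may have been observed. That stands for some events. However, Protocol 6.3 lets follow-up of a persisting toxicity stop once no further improvement is expected, and Protocol 8.1.4.2 ends recording of non-serious AEs when a new anticancer therapy starts. Events left open in these ways would still run to death under 5.3.1.

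Third, the reach is small. Duration is descriptive and limited to AEs of special interest, and only unique or last-of-series events are imputed. Incidence and grade tables do not use the stop date, and SAP 5.2.4 keeps imputed dates out of the last-contact date used for overall survival. All of this stands. SAP 5.3 also defers to a safety rulebook that is not part of the documents, and text near 6.6.1.3 is redacted, so neither a tie-break nor further uses of the stop date can be excluded.

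**Conclusion.** The documents support a conflict of rules. SAP 5.3.1 gives a stop date that depends on vital and withdrawal status, SAP 6.6.1.3 gives one that does not, and no precedence is stated. If the 5.3.1 dates feed the duration formula, the descriptive by-arm durations of AEs of special interest include unobserved time for patients who die well after their AE follow-up ends.

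A reader might go further and infer that durations in patients who died will run months past AE collection, or that the longer-surviving arm will show longer AEs. The documents support neither. The first assumes that 5.3.1 governs, that collection ends at day 28, and that death comes long after last dose. The second ignores two opposing effects: under the design assumptions the glasdegib arm has fewer deaths, but they come later. The net direction is not determined.

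The size rests on assumed days and on the unstated gap from last dose to death, so only the range can be given. The point deserves correction because it affects a planned safety comparison and is cheap to settle. It does not touch the primary analysis.

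**What to change.** State in SAP 6.6.1.3 that any AE recorded as ongoing on the CRF is censored by one rule, whatever the patient's vital or withdrawal status, and that the stop date imputed under 5.3.1 is not used for duration. Either of two rules would do:

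- Keep the existing last on-treatment visit. In the example every patient then has 54 days.
- Use the earliest of death, data cutoff, and the later of the end of the on-treatment period (SAP 3.5) and the last AE collection or follow-up date. This keeps follow-up collected beyond 28 days. In the example, with no later AE follow-up and cutoff after Day 148, it gives at most 89 days.

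In both cases the date must not fall before AE onset. This matters for events in the transplant period, which can begin after the pre-transplant on-treatment period has closed. Flag the date as censored, and cross-refer between the two sections.

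The cost is a few lines of SAP text and a small change to the dataset derivation, with no new data. The downside is that unresolved events are reported as censored, with shorter values for some patients who died.

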## Other Missing or Partial Dates

Imputation methods for other partial dates are as follows:

- If the day of the month is missing for a start date used in a calculation, the first day of the month will be used to replace the missing date.
- If both the day and month are missing for a start date, the first day of the year is used.
- For stop dates, the last day of the month, or last day of the year is used if the day or day and month are missing, respectively.
- If the date is completely missing, no imputation will be performed.

### 5.3.2. Missing Toxicity Grade of Adverse Events

During Study Treatment: If no toxicity grade is available or the grade is reported as unknown for an adverse event during the study treatment, then the event will be considered treatment emergent.

In summaries which present maximum toxicity grade, the maximum of non-missing grades will be displayed. Missing grade will only be displayed for cases where a patient reported only one event and the grade is missing.

### 5.3.3. Missing Pharmacokinetic (PK) Data

#### Concentrations below the limit of quantification

For all calculations, figures, and estimation of individual pharmacokinetic parameters, all concentrations assayed as below the level of quantification (BLQ) will be set to zero. In log-linear plots these values will not be represented. The BLQ values will be excluded from calculations of geometric means and their confidence intervals. A statement similar to ‘All values reported as BLQ have been replaced with zero’ should be included as a footnote to the appropriate tables and figures. In listings BLQ values will be reported as below limit of quantification (“<LLOQ”), where LLOQ will be replaced with the corresponding value from the analytical assay used.

#### Deviations, Missing Concentrations and Anomalous Values

In summary tables and plots of median profiles, concentrations will be set to missing if one of the following cases is true:

- A concentration has been reported as ND (ie, not done) or NS (ie, no sample);
- A deviation in sampling time is of sufficient concern or a concentration has been flagged as anomalous by the clinical pharmacologist.

Summary statistics will not be presented at a particular timepoint if more than 50% of the data are missing. For analysis of pharmacokinetic concentrations, no values will be imputed for missing data.

#### 5.3.4. Missing ECG Data

For ECG analyses, no values will be imputed for missing data (except HR values that can be derived from RR values, if present. If both RR and HR values are missing, QTcB and QTcF will not be determined). In case of missing HR value, HR (bpm) will be derived as  $(60/RR \text{ [sec]})$ , if RR is collected.

If one or two of the triplicate measurements for an ECG parameter are missed, the average of the remaining two measurements or the single measurement can be used in the analyses. If all triplicate measurements are missing at a timepoint for an ECG parameter, no values will be imputed for this timepoint. If the triplicate needs to be repeated because of an artifact, then the repeated triplicate will be reported on an unscheduled CRF page. Based on a review of the data these unscheduled assessments may be used in place of the assessments at the nominal time. Data review and consultation with the study team is required to flag these cases.

CCI

## 6. ANALYSES AND SUMMARIES

Analyses for the intensive and non-intensive chemotherapy studies will be conducted separately and independently. Unless otherwise stated, stratified analysis will be stratified based on ELN genetic risk, age  $\leq 60$  vs  $> 60$  years, and region (rest of world [ROW] vs China) for the intensive patients, and ELN genetic risk and age  $< 75$  vs  $\geq 75$  years for the non-intensive patients. The rate of stem cell transplantation is expected to be much lower for sites in China versus the ROW thus region is being added as a stratification factor for the intensive study analyses. The rate of stem cell transplantation is expected to be low in all regions in the non-intensive study.

### 6.1. Primary Endpoint - Overall Survival

The primary efficacy analysis will compare OS between the experimental arm and the control arm, and will be performed using a one-sided stratified log-rank test. The primary population for the analysis will be the FA set. Strata will be based on those specified in the randomization system including region for the intensive study.

OS is defined as the time from randomization to the date of death due to any cause. Patients last known to be alive will be censored at date of last contact (see [Section 5.2.4](#)). OS will be summarized in months:

$$\text{OS (months)} = [\text{date of death or censoring} - \text{randomization} + 1] / 30.4375.$$

The treatment effect will be estimated using a Cox's PH model stratified by the randomization strata and region for the intensive study to calculate the hazard ratio. Each stratum will define a separate baseline hazard function (using the 'STRATA' statement in SAS PROC PHREG), ie, for the i-th stratum the hazard function is expressed as:  $h(i;t) = h(i,0;t) \exp(x\beta)$ , where  $h(i,0;t)$  defines the baseline hazard function for the i-th stratum and  $x$  defines the treatment arm (0=control arm, 1= experimental arm) and  $\beta$  is the unknown regression parameter. Ties will be handled using the Efron method as an approximation to the exact method (Ties=EFRON option in SAS PROC PHREG).

OS time associated with each treatment arm will be summarized using the Kaplan-Meier method (product-limit estimates) and displayed graphically where appropriate. CIs for the 25th, 50th, and 75th percentiles will be reported. Repeated confidence interval will also be provided, to account for alpha spending. The Cox PH model will be fitted to compute the treatment HRs and the corresponding 95% CIs. In addition, the median OS and its two-sided 95% CI using the Brookmeyer and Crowley method will be provided for each stratum within each treatment arm separately. The HR and its two-sided 95% CI will be provided for each stratum as well.

The OS rate at 12, 24 and 36 months will be estimated with corresponding two-sided 95% CIs for the intensive chemotherapy patients. The OS rate at 6, 12, and 18 months will be estimated with corresponding two-sided 95% CI for the non-intensive chemotherapy patients. The CIs for the median will be calculated according to Brookmeyer and Crowley and the CIs for the survival function estimates at the timepoints defined above will be derived using the log(-log) method according to Kalbfleisch and Prentice (conftype=loglog default option in SAS Proc LIFETEST). The estimate of the standard error will be computed using Greenwood's formula.

Frequency (number and percentage) of patients with an event (death) and censoring reasons will be presented by treatment arm. Censoring reasons are as follows:

- Alive;
- Withdrawal of consent;
- Lost to follow-up.

The OS time or censoring time and the reasons for censoring will also be presented in a patient listing.

Should over-stratification prevent model convergence or there exists large imbalance in the distribution (eg, 90% or more subjects from one strata level), the intermediate and adverse ELN risk groups may be pooled in the analysis.

### **Time of Follow-Up for OS**

A Kaplan-Meier summary table for OS follow-up duration will also be generated to assess the follow-up time in the treatment arms reversing the OS censoring and event indicators.

CCI [REDACTED]

[REDACTED]

| [REDACTED]

| [REDACTED]

| [REDACTED]

| [REDACTED]

| [REDACTED]

| [REDACTED]

[REDACTED]

[REDACTED]

[REDACTED]

[REDACTED]

[REDACTED]

CCI [REDACTED]

[REDACTED]

[REDACTED]

- [REDACTED]
- [REDACTED]
- [REDACTED]

[REDACTED]

[REDACTED]

[REDACTED]

## 6.2. Secondary Endpoints

### 6.2.1. Fatigue

The “Fatigue” single-item from the MDASI-AML/MDS questionnaire is the key secondary endpoint. Similar to analysis of the primary endpoint, the analysis of Fatigue will be conducted separately and independently across the two patient populations (intensive or non-intensive patients). There are two steps of the analysis of Fatigue. If the primary endpoint of OS is met in one population, the hypothesis testing described in Step 2 of this section will be carried out in that population. The overall Type I error is preserved by following this pre-specified hierarchical testing sequence (ie, OS followed by Fatigue).

**Step 1:** A repeated measures model will be used to determine Clinically Important Responder (CIR) within each patient population. We use the change in Fatigue from baseline as the outcome and SGIC-S (Subject Global Impression of Change using PGIS) score (defined below) as the anchor. Note that Fatigue and PGIS are collected following the same schedule and treatment assignment is not a covariate in the model. All available post-baseline data up to Week X will be used (X=8 for intensive patients, X=12 for non-intensive patients). A window of +/-3 days will be applied. If more than one assessment are available in a week, the average value will be used.

A SGIC-S score with three possible values (-1, 0, and 1, treated as continuous variable) will be derived for each subject at each week post-baseline, from Week 1 through Week X, as follows:

- a. SGIC-S = -1, if post-baseline PGIS minus PGIS at baseline is positive (this means *worse*);
- b. SGIC-S = 0, if post-baseline PGIS minus PGIS at baseline is zero (ie, no change, this means *the same*);
- c. SGIC-S = 1, if post-baseline PGIS minus PGIS at baseline is negative (this means *better*).

The predicted change in Fatigue score corresponding to one unit difference on SGIC-S is the threshold for “responder” vs “non-responder”. All patients with change in Fatigue at Week X (X=8 for intensive patients, X=12 for non-intensive patients) at or below the threshold (note that lower values suggest lessening of Fatigue) will be defined as responders.

As a supportive analysis, a SGIC-C (Subject Global Impression of Change using PGIC) score with three possible values (-1, 0, and 1, treated as continuous variable), derived below, will be used in place of SGIC-S in the repeated measures model. Note that PGIC is collected on the same schedule as Fatigue other than there is no assessment of PGIC at baseline.

- a. SGIC-C = -1, if PGIC is 5 or more (this means *worse*);
- b. SGIC-C = 0, if PGIC is 4 (ie, no change, this means *the same*);
- c. SGIC-C = 1, if PGIC is 3 or less (this means *better*).

Additional details of the CIR can be found in the Appendix, where potential sensitivity analyses treating SGIC-S and SGIC-C as categorical variables are also described.

**Step 2:** A formal testing of proportion of responders at Week X (using a 1-sided Cochran Mantel Haenszel [CMH] test, stratified by ELN risk, age [age  $\leq 60$  vs  $>60$  years for the intensive patients, and age  $<75$  vs  $\geq 75$  years for the non-intensive patients], and region [ROW vs China for intensive patients only) will only be conducted in one population if the primary OS endpoint is met in that population (intensive or non-intensive patients). The risk ratio and 2-sided 95% CI will be summarized.

The proportion of responders by treatment arm will be estimated with a 2-sided 95% CI (using normal approximation). The proportion and 2-sided 95% CI (using exact method) of responders for each stratum by treatment arm will also be provided.

In addition to the above responder analyses, analysis of Fatigue will also be supplemented with cumulative distribution function (CDF) and probability density function (PDF) of change in Fatigue score from baseline to Week X. The change in Fatigue at Week X will be plotted on the X-axis while its CDF or PDF will be plotted on the Y-axis.

If the Week X PRO assessment is missing, then the next available completed PRO assessment will be used.

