### 9.3.2. Analysis of Secondary Endpoints

All secondary PRO and efficacy endpoints will be based on the FAS unless stated otherwise.

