#### Fatigue

The key secondary PRO endpoint based on the Fatigue single-item from the MDASI-AML/MDS questionnaire will be analyzed for proportion of responders (defined below) at week 12 for non-intensive patients and week 8 for intensive chemotherapy patients. The proportion of responders will be estimated with a 2-sided 95% CI (using normal approximation). The proportion and 2-sided 95% CI (using exact method) of responders for each stratum will also be provided. A hierarchical testing procedure will be followed, namely, a formal testing of proportion of responders (using a 1-sided Cochran Mantel Haenszel [CMH] test, stratified by ELN genetic risk, age [age ≤60 vs >60 years for the intensive patients, and age <75 vs ≥75 years for the non-intensive patients]), and region [ROW vs China for intensive patients only]) will only be conducted in one population if the primary OS endpoint is met in that population (intensive or non-intensive treatment). The risk ratio and 2-sided 95% CI will also be summarized.

Responder definition will be determined via anchor-based methods using PGIS (primary) and PGIC (supportive), which will be supplemented with cumulative distribution functions (CDF) and probability density functions (PDF). Detailed description of the methodology will be in the statistical analysis plan.

CDF and PDF will be created using individual change from baseline for the fatigue item score from the MDASI-AML/MDS at week 8 for intensive chemotherapy patients and at week 12 for non-intensive patients.

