### 3.4. Baseline Variables

The date of first dose (start date) of study treatment is the earliest date of non-zero dosing of any study drug. The date of last dose of study treatment is the latest date of non-zero dosing of any study drug.

No windowing will be applied when defining baseline. Any deviations from the protocol specified window will be documented as protocol deviations.

For efficacy endpoints (except Fatigue) and baseline characteristics the last non-missing assessment prior to randomization will serve as the baseline assessment. For fatigue, similar to other PRO endpoints, the last non-missing measurement on the day of the first dose of study treatment will serve as baseline (note that PRO endpoints are collected prior to study drug dosing on the same day).

For safety (including Eastern Cooperative Oncology Group (ECOG) performance status) the last non-missing assessment performed on or prior to date of the first dose of study treatment (or prior to randomization for patients randomized but not dosed) will serve as the baseline assessment. If there are no observations meeting these criteria, then baseline is considered missing.

For PRO, the measurement, the day of the first dose of study treatment will be used as the baseline measurement. If there are no observations meeting this criteria, then baseline is considered missing.

Triplicate ECGs are collected; therefore the baseline for each ECG measurement is the average of the pre-dose measurements on the baseline day. Unscheduled assessments will not be included in the calculation of the average. The average of the replicate measurements will be determined after the derivation of the individual parameters at each timepoint.

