### **4.1. Full Analysis Set**

The Full Analysis (FA) set will include all randomized subjects. Subjects will be classified according to the treatment assigned at randomization.

Randomized but not treated patients will be reported under their randomized treatment group for the full analysis set. The FA set will be the primary population for evaluating all efficacy and PRO endpoints CCI [REDACTED] and patient characteristics.

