### 5.2.9. Analyses for Categorical Data

Qualitative variables will be summarized by frequency counts and percentages. Unless otherwise specified, the calculation of proportions will include the missing category. Therefore counts of missing observations will be included in the denominator and presented as a separate category.

In case the analysis refers only to certain visits, percentages will be based on the number of patients with an assessment at that visit, unless otherwise specified.

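### The formal Fatigue responder test is valid but leaves out baseline fatigue; adjusting for it is a cheap improvement that would probably gain some power (minor)

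*SAP*

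**What the plan says.** SAP 6.2.1 works in two steps. Step 1 estimates a threshold from the trial's own data, without treatment in the model. Patients whose change from baseline in the 0-10 Fatigue item at Week 8 (intensive) or Week 12 (non-intensive) is "at or below the threshold (note that lower values suggest lessening of Fatigue) will be defined as responders". Step 2 is "A formal testing of proportion of responders at Week X (using a 1-sided Cochran Mantel Haenszel [CMH] test, stratified by ELN risk, age", with region (rest of world or China) added in the intensive study. Protocol 9.3.2 has the same test: "a formal testing of proportion of responders (using a 1-sided Cochran Mantel Haenszel". It is run in a study only if OS is met there.

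Baseline fatigue is available: under SAP 3.4, "the last non-missing measurement on the day of the first dose of study treatment will serve as baseline". It can also be absent: "If there are no observations meeting this criteria, then baseline is considered missing". SAP 6.2.6.1 plans a mixed model of the same item with baseline as a covariate, but that model is not in the testing hierarchy.

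On the patients to be counted, protocol 9.3.2 says "All secondary PRO and efficacy endpoints will be based on the FAS unless stated otherwise", and SAP 4.1 adds "Randomized but not treated patients will be reported under their randomized treatment group for the full analysis set". SAP 5.2.9 has a general default for visit-specific summaries, that "percentages will be based on the number of patients with an assessment at that visit". SAP 6.2.1 replaces a missing Week X score with the patient's next completed questionnaire, but does not say how a patient with no later score is counted.

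**The concern.** A responder is defined by change from baseline on a scale with a floor at 0. A patient who starts below the size of the required drop cannot respond on either arm, and above the floor the chance of a large drop still depends on the starting value. Baseline fatigue is therefore likely to predict the outcome well, and the data are already collected. The one Fatigue test that can support a formal claim does not use it, while a supportive model of the same item does. At stake is some of the chance of detecting a real fatigue benefit in a study where OS has been met.

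**Working it through.** **The plan's own figures.** The only sizing figures are for OS. Schoenfeld's formula, 4(1.960+1.282)²/(ln HR)², gives 42.03/0.1604, or 263 deaths, at HR 0.67 (stated 267), and 42.03/0.1992, or 212 deaths, at HR 0.64 (stated 220). With the stated boundaries, power is 89.5% and 90.6%, so these figures hold. For Fatigue the documents give no SD, correlation, threshold, responder rate, missing rate or numerical alpha.

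**The floor.** With baseline b, the lowest possible change is -b. A required drop of c therefore needs b ≥ c. With an assumed SD of 2.7 and a mean baseline of 4.5, 7-8% of patients cannot respond at a threshold of -1 and 13-15% at -2. With a mean of 3.0, 28-31% cannot respond at -2.

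**How far baseline predicts change.** If baseline and follow-up have equal variance and correlation r, and rounding and the floor are ignored, the correlation of change with baseline is -√((1-r)/2). This is -0.59 at r = 0.3, -0.50 at 0.5 and -0.32 at 0.8. The gain should therefore shrink as r rises.

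**Power by simulation.** Assumed inputs: mean 4.5, SD 2.7, true shift 0.9 points, 1-sided alpha 0.025, n = 320 (6 strata) and 400 (12 strata). The adjusted test is the score statistic from a logistic model with baseline and the stratification factors. It is referred to its mean and variance under re-randomisation within strata, with a normal reference. Results at cut-off -2, with 2000 replicates per cell:

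| Setting | r | CMH | Adjusted | Gain (points) |
|---|---|---|---|---|
| Non-intensive, assessed only, 15% missing | 0.3 | 0.413 | 0.496 | 8.3 |
| | 0.5 | 0.516 | 0.607 | 9.1 |
| | 0.8 | 0.840 | 0.868 | 2.8 |
| Intensive, assessed only, 15% missing | 0.3 | 0.486 | 0.610 | 12.4 |
| | 0.5 | 0.620 | 0.706 | 8.6 |
| | 0.8 | 0.910 | 0.936 | 2.6 |
| Non-intensive, all randomised, 30% missing as non-response | 0.3 | 0.308 | 0.348 | 4.0 |
| | 0.5 | 0.399 | 0.434 | 3.5 |
| | 0.8 | 0.734 | 0.757 | 2.3 |
| Intensive, all randomised, 30% missing as non-response | 0.3 | 0.346 | 0.394 | 4.8 |
| | 0.5 | 0.484 | 0.522 | 3.8 |
| | 0.8 | 0.824 | 0.842 | 1.8 |

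Under the null (4000 replicates, 12 scenarios) the adjusted test rejected at 0.025 on average (range 0.020-0.029) and the CMH at 0.024.

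**Wider ranges for the same test:**
- Assessed only, 15% missing: about 0 to 13 points.
- All randomised, 15-30% missing at random: 1 to 8 points.
- Missingness following worse baseline fatigue: -0.4 to +2.6 points. High-baseline patients are the likelier responders, but here they are also the likelier to be missing and so counted as non-responders, which cancels the information in baseline.
- Null rejection: 0.024-0.027.

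A smaller run with 399 actual re-randomisations per data set (non-intensive, all randomised, 30% missing) gave +0.3 to +3.1 points with random missingness and -1.4 to +1.6 when missingness followed worse baseline. Monte Carlo error there is up to about 1 point, and so few re-randomisations cost a little power.

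**Form of adjustment.** Adding four baseline bands to the CMH strata gained only -1 to +11 points where the logistic score test gained 4 to 15. A model is the better route, since the intensive study already has up to 12 strata. The model-based score test without re-randomisation shows slightly larger gains than those above, but about 1 point of that reflects a null rate of 0.027 against 0.025.

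**The case against.** The best counter-argument is that this is a preference. The stratified CMH is coherent with the response analyses, a baseline-adjusted model of the same item is already planned, and a key secondary test need not have maximum power. That stands as far as calling the plan wrong goes, and this point does not call it wrong.

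Second, the gain depends on the denominator. The full-analysis-set statements, which SAP 6.2.6 repeats for all PRO analyses, carry more weight than a default for percentages in SAP 5.2.9. The smaller gains are then the relevant ones. Random missingness is also doubtful: under the SAP's exponential medians, deaths by Week 12 (2.76 months) would be 1 - 2^(-2.76/10.4) = 17% of control and 1 - 2^(-2.76/16.2) = 11% of experimental non-intensive patients. Both points stand. The rule that takes the next completed questionnaire would lower the missing rate, but was not simulated.

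Third, the regulator has shaped this analysis. The protocol's document history records that Amendment 2 specified the fatigue analysis at FDA request and that Amendment 3 clarified the PRO analyses at regulatory request. SAP Table 1 records PRO revisions after FDA comments. This raises the cost of a change but does not rule it out.

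A reader might infer more: that the CMH is biased or inflates type I error without baseline, or that Fatigue is underpowered. The documents support neither. Randomisation protects the CMH, whose simulated null rates lie around 0.025, and no fatigue power is claimed that could be missed.

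**Conclusion.** A minor, optional improvement. The planned test is valid but omits an available covariate that bears directly on who can respond. For the re-randomised test the likely gain is roughly 2 to 13 points if only assessed patients count with 15% missing (about 0 to 3 at correlation 0.8). It is about 1 to 8 points if all randomised patients count with 15-30% missing at random as non-response, and about zero if missingness follows worse baseline fatigue. All of this rests on assumed fatigue inputs and one assumed effect size; the direction is better supported than the size. Type I error stays near 0.025. The test matters only if OS is met, and OS and its error control are unaffected.

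**What to change.** Before unblinding, amend SAP 6.2.1 Step 2:

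- Make the formal 1-sided test a test of treatment from a logistic model with continuous baseline fatigue, ELN risk, age and (intensive only) region. Take the p-value by re-randomising within the randomisation strata, following the actual allocation scheme, or from the normal approximation to it.
- Use the same patients as the CMH, and state who they are. Apply the rule for a missing Week X score first. If patients without a baseline count as non-responders, fill the covariate with the mean pooled over both arms. A missing-value indicator would not work, because all these patients are non-responders and the term is perfectly separated.
- Report a standardised risk ratio with 95% CI. Keep the planned CMH as the fallback for non-convergence and as a sensitivity analysis.

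The cost is a SAP amendment and some programming, including the re-randomisation; no new data are needed. Protocol Section 9 lets the SAP modify the protocol's analyses and requires a protocol amendment only for major changes to the primary endpoint. The CMH is also written in protocol 9.3.2 and the regulator took part in this analysis, so the change should be documented and shared with it. The downside is that the test becomes model-assisted and may disagree with the CMH.
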